## LIST OF ABBREVIATED TERMS

AE	Adverse Event	PMCF	Post Market Clinical Follow-Up
ACA	Anterior Cerebral Artery	PTFE	Polytetrafluoroethylene
ADAPT	A Direct Aspiration First Pass Technique	RBC	Red Blood Cell
ADE	Adverse Device Effect	RCT	Randomized Control Trial
AIS	Acute Ischemic Stroke	rtPA	Recombinant Tissue Plasminogen Activator
ASPECTS	Alberta Stroke program early CT score	SAE	Serious Adverse Event
BA	Basilar Artery	SADE	Serious Adverse Device Effect
CA	Competent Authority	SAH	Subarachnoid Hemorrhage
CBV	Cerebral Blood Volume	SAP	Statistical Analysis Plan
CRF	Case Report Form	SBP	Systolic Blood Pressure
CT	Computed Tomography	SDV	Source Data Verification
CTA	Computed Tomography Angiography	SOC	Standard of Care
DBP	Diastolic Blood Pressure	SOP	Standard Operating Procedure
EC	Ethics Committee	SVS	Susceptibility Vessel Sign
eCRF	Electronic Case Report Forms	VA	Vertebral Artery
EDC	Electronic Data Collection	WBC	White Blood Cell
GCE	Geometric Clot Extractor		
GCP	Good Clinical Practice		
IC	Informed Consent		
ICA	Internal Carotid Artery		
ICF	Informed Consent Form		
ICH	International Council for Harmonization		
IFU	Instructions for Use		
IV	Intravenous		
IV-tPA	Intravenous tissue plasminogen activator		
LVO	Large Vessel Occlusion		
MCA	Middle Cerebral Artery		
mITT	Modified Intention to Treat		
MM	Medical Monitor		
MRA	Magnetic Resonance Angiography		
MRI	Magnetic Resonance Imaging		
mRS	Modified Rankin Scale		
mTICI	Modified Thrombolysis in Cerebrovascular Infarction		
NIHSS	National Institute of Health Stroke Scale		
OD	Outer Diameter / Outside Diameter		
PI	Principal Investigator		

## PROTOCOL SYNOPSIS

Study Title	Post Marketing Study of Patients to Evaluate NIMBUS Revascularization Effectiveness with Challenging Occlusions. (Protocol#: CNV_2018_01)	
Short Title	SPERO	
Study Sponsor	CERENOVUS acting through Neuravi Ltd. [name]	
Laboratories	
Imaging Core Lab: [REDACTED]
 
Central Lab for Clot Analysis: [REDACTED]
	
Study Device	CERENOVUS NIMBUS Geometric Clot Extractor, hereafter referred to as NIMBUS	
Indication	To restore blood flow in patients experiencing an acute ischemic stroke due to a large vessel neurovascular occlusion. The Device is designed for use in the anterior and posterior neurovasculature in vessels of diameter 1.5 mm to 5.0 mm, such as the internal carotid artery, the M1 and M2 segments of the middle cerebral artery, the A1 and A2 segments of the anterior cerebral artery, the basilar, the posterior cerebral and the vertebral arteries. The Device should only be used by physicians trained in neurointerventional catheterization and the treatment of ischemic stroke.	
Study Design	This is a prospective, multi-center, single-arm, observational post market study that will consecutively enroll up to 50 subjects treated with NIMBUS at up to 10 sites in Europe. Follow up with subjects will occur over 3 months at 24 hours, and 90 days post procedure.	
Sample Size	Approximately 50 subjects will be consecutively enrolled into the study which will involve treatment with NIMBUS.	
Number of Sites	Approximately 10 clinical sites in the EU	
Study Duration	Start Date: Q4 2018	End Date: Q2 2021
Study procedures	Subjects will have challenging occlusions, with mTICI $\leq$ 2a post one, or two passes, of another Mechanical Thrombectomy device. Any commercially available Mechanical thrombectomy device (i.e. either aspiration or Stent-retriever other than NIMBUS) may be used during the first and up to two vessel clearance attempts. The physician may use his own discretion on whether to introduce the NIMBUS after one failed vessel clearance attempt, or after two.	

	
The NIMBUS must be used no later than the overall third procedural pass for the patient to be eligible. Up to 50 subjects will be treated with the NIMBUS.
 
Once the decision has been made to use NIMBUS, it is used for up to three passes. After the third pass with the NIMBUS, if the physician would like to utilize another device/technique for treatment, they may. Angiographic imaging will be collected per every pass for subsequent review by an independent Imaging Core Lab. Clot will also be collected per every pass for analysis in an independent Central Lab.
 
After the procedure, subjects will be followed for 90 days per the schedule below:
 
 
1. Study procedure
 
2. 24 Hour Follow-up (+/- 8 hrs)
 
3. 90 Day Follow-up (+/- 14 days)
 

Primary Objective	The objective of this study is to assess the efficacy of the NIMBUS in a real-world setting in patients where the first one or two passes with another Mechanical thrombectomy therapy have not achieved mTICI 2b or better. The rate of effectiveness achieved will be considered as we design further studies. The study will also evaluate and report on clot characteristics and clinical outcomes.
Primary Endpoint	Successful Revascularization (mTICI $\geq$ 2b) with NIMBUS as determined by an Independent Core Lab.
Secondary Endpoints	
 
1. Successful Procedural Revascularization (final mTICI <math>\geq</math> 2b).
 
2. Excellent Procedural Revascularization (final mTICI <math>\geq</math> 2c).
 
3. First Pass Revascularization using Nimbus (mTICI <math>\geq</math> 2b).
 
4. Occurrence of Embolization to a New Territory (ENT).
 
5. Symptomatic Intracerebral Hemorrhage (sICH) at 24 hours specified according to the Heidelberg Bleeding Classification (HBC).
 
6. 90 Day All-Cause Mortality.
 
7. Modified Rankin Scale (mRS) of <math>\leq</math> 2 at 90 days.
 

Ancillary Endpoints	
 
1. Clot Analysis
 
2. Hospitalization Analysis
 

Inclusion Criteria	
All Subjects:
 
 
1. Age <math>\geq</math> 18
 
2. The subject or the subject's legally authorized representative has signed and dated an Informed Consent Form.
 
3. Patient has had one or two passes of another mechanical thrombectomy device without achieving mTICI 2b or better and continues to have angiographic confirmation of a Large Vessel Occlusion (LVO) in the same vessel.
 

[figure not shown]
 A Large Vessel Occlusion (LVO) is an occlusion in the ICA, MCA, ACA, VA, or BA.

	
 
4. mRS 0-1 prior to this stroke.
 
5. NIMBUS is used on the second or third overall pass to attempt revascularization.
 

Exclusion Criteria	
 
1. Currently participating in an investigational (drug, device, etc.) clinical trial that may confound study endpoints. Patients in observational, natural history, and/or epidemiological studies not involving intervention are eligible.
 
2. Confirmation of positive pregnancy test according to site specific standard of care (e.g. test, verbal communication).
 
3. All patients with severe hypertension on presentation (SBP > 220 mmHg and/or DBP > 120 mm Hg). All patients, in whom intravenous therapy with blood pressure medications is indicated, with hypertension that remains severe and sustained despite intravenous antihypertensive therapy (SBP > 185 mmHg and/ or DBP > 110 mmHg).
 
4. Known cerebral vasculitis.
 
5. Known cancer with life expectancy less than 12 months.
 
6. Stenosis, or any occlusion, in a proximal vessel that requires treatment or prevents access to the site of occlusion.
 
7. Intracranial stenosis that prevents access to the site of occlusion.
 
8. Computed tomography (CT) or Magnetic Resonance Imaging (MRI) evidence of recent/ fresh hemorrhage on presentation.
 
9. Baseline computed tomography (CT) or MRI showing mass effect or intracranial tumor (except small meningioma).
 
10. Evidence of dissection in the extra or intracranial cerebral arteries.
 
11. Occlusions in multiple vascular territories (e.g., bilateral anterior circulation, or anterior/posterior circulation).
 

Sample Size and Power Calculation	
There is no hypothesis testing for this post-market study. Up to 50 treated subjects are deemed sufficient to evaluate the performance of NIMBUS. These results may be used to inform further studies.
 
Approximately 50 subjects will be consecutively enrolled using commercially available Mechanical Thrombectomy devices during the initial one, or two, Mechanical thrombectomy passes. With an enrolled sample size of 50 and an attrition rate of no more than 10%, the precision (margin of error) for the primary endpoint is anticipated to be around 10.1% based on 2-sided 95% confidence intervals, where the primary endpoint rate is estimated to be 86%.
 $\text{Margin of error} \approx 1.96 \times SE = 1.96 \times \sqrt{\frac{p(1-p)}{n}} = 1.96 \times \sqrt{\frac{0.86 \times (1-0.86)}{45}} = 10.1\%$ 
where SE denotes the standard error and p denotes the proportion of subjects who achieve the primary endpoint.

Statistical Analysis	
Analyses will be presented for approximately 50 subjects treated with NIMBUS.
 
Descriptive summary statistics will be presented for all endpoints. The number and percentage of subjects will be summarized for categorical variables. Descriptive statistics for continuous variables will include the number of subjects, mean, standard deviation, median, minimum and maximum.

-----------------------------	-------------------------------------------------------------------------------------------------------------------------------------------------------------------------------------------------------------------------------------------------------------------------------------------------------------------------------------------------------------------------------------------------

## SCHEMATIC OF STUDY DESIGN

Assessments and imaging performed for the study are part of standard of care (SOC) for stroke treatment, and screening can occur without obtaining consent. Informed consent is mandatory and must be obtained before any data is captured in the electronic Case Report Form (eCRF).

**Footnote 1:** Optional

**Footnote 2:** Mechanical Thrombectomy

**Note 1.** All thrombectomy subjects for whom a second pass with any thrombectomy device was completed will be recorded in the site screening log.

**Note 2.** Informed Consent may be obtained at any point from imaging confirmation of an Acute Ischemic Stroke through to 7 days post-procedure.

Figure 1: Schematic of Study Design

## SCHEDULE OF ASSESSMENTS

Table 1: Schedule of Assessments

Table Legend: X = Required; O = Optional, to be collected if performed during standard of care	Enrollment			Follow-up	
	Baseline	Procedure	Post-procedure 24hrs (+/- 8 hrs)	90 Day Follow-up (+/- 14 days)	Unscheduled 
Assessments					
ICF	X				
Eligibility Screening	X				
Demographics and Medical History	X				
IV t-PA administration	O				
Imaging 	X	X	X		O
NIH Stroke Scale (NIHSS)	X		X	O	O
Modified Rankin Scale (mRS)	X			X	O
Angiography 		X			
Review of Applicable Adverse Events (AE)		X	X	X	X
Clot Collection 		X			

(1) CT/MR Imaging and angiography will be sent to independent Imaging Core Lab for review.

(2) Due to the emergent nature of AIS, consent may be obtained after the procedure but up to 7 days post-procedure as permitted by the local regulations and EC.

(3) Per pass clot collection to be sent to Central Lab for processing.

(4) If more than one NIHSS was performed during this time period, select the worst (highest) value.

(5) To be evaluated by a qualified evaluator; pre-stroke mRS should reflect the subject's condition just prior to the stroke onset. For example, if the subject was hospitalized during stroke onset, the subject's reason for hospitalization should be taken into account when evaluating the subject's pre-stroke mRS.

(6) Assessments should be completed for unscheduled visits from the time of Discharge up to (but not including) the 90-day Follow-up, where imaging, NIHSS, or mRS is performed as part of stroke management care for the subject.

(7) The 90 day mRS must be performed by a qualified independent evaluator who is not part of the interventional treating team.

# 1 BACKGROUND INFORMATION AND SCIENTIFIC RATIONALE

## 1.1 Background

Acute Ischemic Stroke (AIS) affects approximately 613,000 patients in the European Union and 795,000 patients in the United States, annually [1, 2]. IV thrombolytic therapy remains the standard of care for acute ischemic stroke; however, it is not effective in recanalizing large vessel occlusions (LVOs) [3, 4]. The presence of LVO of a major intracranial artery, most commonly the middle cerebral artery (MCA) or internal carotid artery (ICA), is estimated to occur in approximately one-third to one-half of acute ischemic stroke [5].

Occlusion of the large intracranial arteries in ischemic stroke is associated with significant disability and mortality. Timely revascularization of intracranial artery occlusions is the therapeutic goal in stroke therapy [6]. Currently available treatment strategies aimed at restoring blood flow in acute ischemic stroke patients include thrombolytic agents (such as intravenous (IV) or intra-arterial thrombolysis with recombinant tissue plasminogen activator (rtPA)) and/or neurothrombectomy devices for mechanical clot retrieval, followed by rehabilitation through specialized supportive care.

IV lytics have several limitations; one being narrow therapeutic window. They are used in Europe and the United States for patients presenting up to 4.5 hours after symptom onset. Although in the US they are only FDA approved for use in patients presenting up to 3 hours after symptom onset, US national clinical practice guidelines [4, 7] recommend also administering IV lytics in the 3-4.5h window to those patients who meet the ECASS 3 trial inclusion/exclusion criteria [8]. In addition to time constraints, IV thrombolytic therapy has been demonstrated to be less effective in recanalizing proximal large vessel occlusions, such as the ICA and MCA. Since a large percentage of strokes presenting at hospitals are large vessel occlusions, this is an important clinical challenge to address. Additionally, not all patients may be treated with thrombolytic therapy due to contraindications, and so mechanical thrombectomy is a valuable alternative in patients contraindicated to t-PA or where t-PA treatment was not effective.

## 1.2 State of Art

Endovascular mechanical revascularization (thrombectomy) is an increasingly used method for intracranial large vessel recanalization in acute stroke. Currently, a number of mechanical recanalization devices are in clinical use. First generation devices included the Merci Retriever device. Newer devices based on stent-like technology, referred to as “stentriever” or “stent-retrievers”, have displaced these first generation thrombectomy devices for recanalization in acute ischemic stroke. Since the introduction of stent-retrievers, multiple randomized trials showed the efficacy of endovascular therapy in conjunction with IV-tPA over IV-tPA alone in acute ischemic stroke patients [9, 10, 11, 12, 13, 14, 15, 16, 17]. Other RCTs have provided comparative performance of different thrombectomy devices [18, 19, 20, 21].

The following are lists of relevant RCTs grouped as mechanical thrombectomy vs. IV-tPA or grouped as mechanical thrombectomy device vs. comparator device.

### Mech. Thrombectomy vs Medical management or IV-tPA

- MR RESCUE [22]
- IMS III [23]
- Synthesis [24]
- THERAPY [25]
- MR CLEAN [10]
- EXTEND-IA [11]
- REVASCAT [26]
- SWIFT-PRIME [9]
- ESCAPE [27]
- THRACE [14]
- DEFUSE 3 [15]
- PISTE [16]
- DAWN [17]

### Device vs. Device

- SWIFT [18]
- TREVO 2 [19]
- ASTER [20]
- 3D Retriever [21]

While the benefit of mechanical thrombectomy in AIS patients with LVO has been demonstrated in comparison to IV-tPA alone, continuing efforts are made to maximize benefit for patients and reduce complications. These investigations generally seek to determine optimal interaction between thrombectomy device and thrombus to improve successful revascularization rates [20, 21, 28, 29]. Most mechanical thrombectomy techniques may be categorized as follows:

- use of stent retrievers by incorporation of the clot through the stent retriever struts after passive stent opening with subsequent withdrawal of the device, with or without flow arrest by a balloon guide catheter [28, 29],
- A Direct Aspiration First-Pass Technique for thrombectomy (ADAPT) with a large bore aspiration catheter placed at the face of the thrombus [20, 29, 30] - This technique utilizes aspiration as the first approach to revascularize the occluded vessel, and if this strategy fails, then the aspiration catheter is used in conjunction with a stent retriever to obtain revascularization.,
- a combination of stent retriever and aspiration catheter, where the stent retriever is usually withdrawn into an intracranially placed aspiration catheter [21, 29].

More significant though, are the most recent RCTs providing evidence refining patient selection to expand the range of patients benefiting from mechanical thrombectomy [14, 15, 16, 17].

The most significant new literature are the results of the DAWN [17] and DEFUSE 3 [15] trials, which demonstrated significant improvement in clinical outcomes for patients treated with mechanical thrombectomy as late as 6 to 24 hours since last seen well.

The DAWN trial used clinical imaging mismatch (a combination of NIHSS score and imaging findings on CTP or DW-MRI) as eligibility criteria to select patients with large anterior circulation vessel occlusion for treatment with mechanical thrombectomy between 6 and 24 hours from last known to be well. Clinical imaging mismatch criteria were defined in three ways: patients  $\geq 80$  years old were included if NIHSS  $\geq 10$  and infarct volume  $<21$  ml; patients  $<80$  years old were included if NIHSS  $\geq 10$  and infarct volume  $<31$  ml, or if NIHSS  $\geq 20$  and infarct volume of 31ml to  $<51$  ml. The trial demonstrated an overall benefit in functional outcome at 90 days in the patients treated with mechanical thrombectomy compared to patients who received only medical management (mRS score 0–2, 49% versus 13%).

The DEFUSE 3 trial used perfusion-core mismatch and maximum core size as imaging criteria to select patients with large anterior circulation occlusion 6 to 16 hours from last known to be well for mechanical thrombectomy. This trial showed a benefit in functional outcome at 90 days in the treated group (mRS score 0–2, 44.6% versus 16.7%). Benefit was independently demonstrated for the subgroup of patients who met DAWN eligibility criteria and for the subgroup who did not.

### 1.2.1 Performance

In these studies, the proportion of patients experiencing procedural revascularization success (defined as TICI scores of 2b to 3) ranged from 76% in [15] to 85.4% in [20] when reported after all procedures. For the two studies also reporting revascularization success after a set number of passes, it ranged from 63% in [20] to 81.9% in [21]. Patients achieving functional independence (defined as 90-Day mRS scores of 0–2) ranged from 38% in [25] up to 53% in [14]. While these performance results may not convey the entirety of patient benefit, they provide an approximate quantification of the benefit AIS patients may derive from state of the art treatment with mechanical thrombectomy.

## 1.2.2 Safety

Assessing the same studies for safety outcomes, mortality rates three months after procedure ranged from 22.7% at the highest [21] to 12% at its lowest [25]. Symptomatic intracerebral haemorrhage (sICH) ranged from 9.3% at the highest [25] to 0% at its lowest [16]. Other reported complications and adverse events included (highest values shown): ICH of any kind: 46% [20]; parenchymal hematoma: 17.4% [20]; neurological deterioration: 14% [17]; embolization in new territory (ENT): 6% [14]; vascular perforation: 2.6% [20]; dissection: 3% [14]; vascular spasm: 23% [14]; new ischemic stroke in different territory: 9.1% [16]; and access site complications: 2% [14].

## 1.2.3 Unmet needs

Though success rates are high when utilizing mechanical thrombectomy, there are still a proportion of patients for which adequate reperfusion cannot be achieved, certainly, in part, due to the clot not being retrieved. There is a need to study better options for these challenging situations where the current stent retrievers are unsuccessful during the first few attempts at clot removal.

## 1.3 Study Device

### 1.3.1 Description

[figure not shown]
NIMBUS is composed of a self-expanding nitinol cage that engages with a clot upon device deployment. The nitinol cage is connected to the distal end of a tapered (guidewire-like), PTFE coated nitinol shaft, and has radiopaque markers located immediately distal and proximal to the nitinol cage.

NIMBUS is an innovative design, intended to engage with and retain clots of various type and composition.

The design of NIMBUS is shown in Figure 2, with relevant dimensional information and annotated design features. The laser-cut nitinol cage on the NIMBUS device is shaped into two sections, a proximal or “spiral” section, and a distal or “barrel” section. The proximal section has a gradual spiral shape, rather than a straight cylindrical shape. The distal section of the cage is barrel shaped with a truncated distal end. As the microcatheter is retracted, the wider distal section is unsheathed first and begins to expand. This section is designed to facilitate clot entry and engagement within the struts of the cage during expansion of the device within the clot, similar to other stent-retriever devices. The more proximal section of the Nitinol cage is set in a spiral configuration and has a 2-cell circumferential pattern. This design allows deep engagement of clot in smaller vessels, yet also facilitates clot engagement in larger vessels through the OD created by the entire spiral section. Hence, clot may become engaged within the struts of the spiral structure or in the space created within the spiral formation. The NIMBUS nitinol cage design has demonstrated successful removal of both firm and soft clots through both *in vitro* and *in vivo* studies, and the spiral section design, in particular, facilitates removal of fibrin-rich clots which can be challenging in some cases.

The design features of NIMBUS provides physicians with a device offering that is compatible with the various retrieval techniques widely used in mechanical thrombectomy procedures throughout Europe.

NIMBUS is supplied preloaded within an insertion tool – a transparent, PTFE tube incorporating an orange stripe. In use, the physician inserts the insertion tool into the hub of a pre-positioned microcatheter and advances the device through the insertion tool and into the microcatheter. The orange stripe makes the tool easy to identify if needed to reload the device for an additional pass. NIMBUS does not contain any medicinal substances, tissues, or blood products.

**Figure 2: Annotated schematic of NIMBUS components**

1. Shaft/Push wire; 2. Proximal Radiopaque Coil; 3. Nitinol Cage; 4. Gold Markers (X2); 5. Distal Radiopaque Coils (X2)

Dimensions A to E are specified in the IFU.

### 1.3.2 Device Storage and Stability

The NIMBUS device should be stored in accordance with the IFU.

### 1.3.3 Device Acquisition

The CERENOVUS NIMBUS Geometric Clot Extractor (NIMBUS) is CE marked and manufactured by CERENOVUS. The device will be ordered by the sites through standard commercial means. Shipments will not be tracked for this study, devices will be fully traceable though the company's 21 CFR 820 and ISO 13485 complaint quality system.

### 1.3.4 Device Returns

Any suspected device malfunction with NIMBUS should be properly documented on the Electronic Case Report Forms (eCRFs). In the event of a suspected malfunction, the device shall be returned to CERENOVUS per the address below for analysis. Sites will retain tracking information. All study devices should be returned to:

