#### 4.1 Inclusion Criteria

Prior to entry in this study, patients must meet **ALL** of the following criteria:

1. Age  $\geq$  18.
2. The subject or the subject's legally authorized representative has signed and dated an Informed Consent Form.
3. Patient has had one or two passes of another mechanical thrombectomy device without achieving mTICI 2b or better and continues to have angiographic confirmation of a Large Vessel Occlusion (LVO) in the same vessel.
4. mRS 0-1 prior to this stroke.
5. NIMBUS is used on the second or third overall pass to attempt revascularization.

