### 7.1.6 Device Deficiency, Device Malfunction, and Use Error

All study device deficiencies shall be documented in the eCRF throughout the clinical investigation and appropriately managed by the Sponsor. If a study device deficiency is detected or suspected that could have led to an SADE, it should be documented on the appropriate eCRF, and the device failure and AE (if applicable) must be reported to the Sponsor within 72 hours upon study site staff awareness. All non-study device malfunctions should be reported via the manufacturer's complaints handling process.

- A **device deficiency** is defined as inadequacy of a medical device with respect to its identity, quality, durability, reliability, safety or performance.
  - **Note:** Device deficiencies include malfunctions, use errors, and inadequate labeling.
- **Device malfunction** is defined as a failure of an investigational medical device to perform in accordance with its intended purpose when used in accordance with the IFU or clinical investigation plan.
- **Use error** is defined as the act or omission of an act that results in a different medical device response than intended by the manufacturer or expected by the user.
  - **Note 1:** Use error includes slips, lapses, and mistakes.
  - **Note 2:** An unexpected physiological response of the subject does not in itself constitute a use error (ISO 14155).

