## 7.7 Device Complaints, Failures, Deficiencies, and Malfunctions

All device complaints, failures, deficiencies (with or without an associated AE), and technical complications must be reported to CERENOVUS Complaint department within **72 hours** of investigator's/Site's knowledge of the event. This device must remain at the site until Sponsor provides instructions on how to return the device for analysis (refer to Section 1.3.4). Another, new device may be used.

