## 5 Analysis Sets

The following analysis sets are defined in the study:

- **Modified Intent-to-Treat (mITT) Analysis Set**

The mITT Analysis Set consists of all subjects who are enrolled into the study, and who have attempted at least one pass with the NIMBUS device (which includes deployment and retrieval with the NIMBUS device).

A subject is considered enrolled in this study after the physician confirms the subject meets all eligibility criteria, and the subject is consented.

- **mRS Analysis Set**

The mRS Analysis Set consists of all mITT subjects who meet the study criteria as defined in protocol section 9.5.

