### 7.10 Additional Analyses

Unless specified otherwise, the following events will be analyzed using the mITT Analysis Set.

- Device deficiency

Subjects with at least one device deficiency data from CRF will be listed.

- Protocol deviations

The number of deviations, the number and percentages of subjects with any protocol deviation will be summarized overall and by deviation category.

- NIH Stroke Scale (NIHSS) total score

The NIHSS total score and change from baseline will be summarized at the scheduled visits with observed data.

- mTICI scores

All mTICI scores will be summarized by pass and at the end of study procedure using the assessments from the core lab.

- First pass effect using NIMBUS

To investigate the first pass effect using NIMBUS, the number and percentage of subjects by mTICI score(including combinations of  $mTICI \geq 2b$ ,  $mTICI \geq 2c$ ) following the first pass of NIMBUS will be summarized using the assessments from the core lab.

A shift table of mTICI scores from pre-first NIMBUS pass to post-final NIMBUS pass will be summarized, excluding the end of procedure mTICI scores.

Similarly, a shift table of mTICI scores before and after the first NIMBUS pass will be summarized as well.

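### The SAP lists device deficiencies for the mITT set by default, so a NIMBUS failure that keeps a subject out of mITT can go unlisted

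*Protocol*

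**What the plan says.** **Recording.** Protocol 1.3.4 states: "Any suspected device malfunction with NIMBUS should be properly documented on the Electronic Case Report Forms (eCRFs". Protocol 7.1.6 is as broad: "All study device deficiencies shall be documented in the eCRF throughout the clinical investigation". Neither makes the record depend on how far the device got.

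**Reporting.** SAP 7.10 opens with "Unless specified otherwise, the following events will be analyzed using the mITT Analysis Set". Its device-deficiency item then says only "Subjects with at least one device deficiency data from CRF will be listed". No other set is named for that item.

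**The set.** SAP 5, in the same words as Protocol 9.5, limits mITT to enrolled subjects "who have attempted at least one pass with the NIMBUS device (which includes deployment and retrieval with the NIMBUS device". The only other set, the mRS Analysis Set, is a subset of mITT. Neither document defines a safety, as-treated or all-enrolled set. SAP 7.6 names no analysis set for adverse events.

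**Entry to the study.** Inclusion criterion 5 (Protocol 4.1) reads "NIMBUS is used on the second or third overall pass to attempt revascularization" and does not say what counts as use. Under Protocol 6.1 and SAP 5, enrolment needs confirmed eligibility and consent. Protocol 6.1 also has every subject with written consent entered in the eCRF, whether or not that subject goes on to participate.

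**The concern.** A list of device failures should not depend on the device having worked well enough to be deployed and retrieved. Here the collection rule has no such condition, while the reporting rule takes one over from a set that also serves the primary efficacy endpoint. In a post-market study of one device, with at most 50 subjects, a single device failure matters to the reader. If membership of the listing turns on how a programmer reads the mITT definition, that choice could be made after the failures are known.

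The issue is the population for device-safety output. It would remain if the efficacy denominator were agreed to be right.

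**Working it through.** **1. The plan's own figures.** The documents give no malfunction rate, so there is no planned figure to reproduce on this point. The only computed design figure is the margin of error in Protocol 9.6 and SAP 6: 1.96 × √(0.86 × 0.14 / 45) = 1.96 × 0.0517 = 10.1%. It reproduces and is not affected.

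**2. Which failures reach the listing.** Protocol 1.3.6 describes delivery, deployment and retrieval as separate steps (1.3.6.1 to 1.3.6.3). The parenthesis in the mITT definition names only the last two. For a consented subject with a recorded NIMBUS deficiency:

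| Situation | In mITT? | Listed? |
|---|---|---|
| Failure, then another qualifying NIMBUS pass | Yes, if enrolled | Yes |
| Failure on a later pass, after a qualifying one | Yes, if enrolled | Yes |
| Only attempt failed during deployment or retrieval | Yes if trying is enough; no if both steps must be completed | Depends on the reading |
| Only attempt failed before deployment, for example in the insertion tool or microcatheter | Doubtful: neither named step began | Probably not |
| As the row above, and NIMBUS judged not used under criterion 5 | No: not enrolled | No |

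The first two rows follow because the listing is by subject and takes anyone with at least one deficiency record. Protocol 7.7 says "Another, new device may be used", which allows the first row but does not ensure it. Protocol 1.4.1 shows that failed delivery is foreseen: it names vessel tortuosity that may stop the device being delivered as a contraindication.

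**3. Illustration of size.** Inputs: the cap of 50 subjects (Protocol 4.4) and an assumed number k of enrolled subjects in the rows that are not listed. Exact (Clopper-Pearson) limits are the 2.5% quantile of Beta(k, 50 − k + 1) and the 97.5% quantile of Beta(k + 1, 50 − k).

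| k (assumed) | Over 50 enrolled (exact 95% CI) | As listed from these subjects |
|---|---|---|
| 1 | 2.0% (0.1 to 10.6) | none among 49 |
| 2 | 4.0% (0.5 to 13.7) | none among 48 |
| 3 | 6.0% (1.3 to 16.5) | none among 47 |
| 5 | 10.0% (3.3 to 21.8) | none among 45 |

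**4. Chance that it arises.** If a proportion r of subjects falls in those rows, the chance of at least one among 50 is 1 − (1 − r)^50. That is 39.5% for r = 1%, 63.6% for 2%, 92.3% for 5% and 99.5% for 10%. These values of r are assumptions.

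The SAP plans a listing without rates or intervals. The percentages only show what one omitted subject is worth.

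**The case against.** **Attempted is not completed.** The mITT definition speaks of an attempted pass. On its plain reading, a NIMBUS that fails to open or cannot be withdrawn has still been attempted, so the subject is in mITT and is listed. This stands for failures during deployment or retrieval, and it is why the point is conditional there. It is weaker for failed delivery, where neither named step began.

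**All enrolled subjects are treated.** SAP 2 says every enrolled subject will be treated with NIMBUS, which suggests that mITT and the enrolled set coincide. But the extra mITT clause has work to do only if some enrolled subjects fail it, and SAP 7.2 tabulates enrolment by site for consented subjects as well as for each analysis set.

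**Undelivered devices may mean no enrolment.** If the device never counted as used, the subject may fail criterion 5. This stands. A listing of enrolled subjects would then still miss the clearest case, so the remedy has to rest on consented subjects.

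**The events are not lost.** Deficiencies also go to the sponsor's complaint department within 72 hours (Protocol 7.7), and SAP 7.6 does not restrict adverse events to mITT. Both are true. They protect surveillance and some harm reporting, but they do not complete the listing in SAP 7.10.

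**Stronger readings.** A reader might infer that mITT plainly demands a completed deployment and retrieval, that the gravest failures are systematically dropped, or that the report would present a deficiency rate of zero. The documents support none of these: the wording is open, deficiencies are not ranked by gravity, and no rate is planned.

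**Conclusion.** The mismatch between the recording rule and the listing rule is real but narrow. A deficiency can be left out of the study listing when both of the following hold:

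- the consented subject's only NIMBUS attempt failed before deployment, or failed during deployment or retrieval and the mITT parenthesis is taken to mean completed steps;
- no other qualifying NIMBUS pass followed.

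The number affected is unknown and may be zero. One such subject among 50 would be 2.0% (exact 95% CI 0.1 to 10.6) against none listed among 49, assuming that the subject was enrolled. The primary endpoint, its precision and the efficacy set are unaffected. The point deserves a change because the correction is cheap and removes a dependence on wording that could otherwise be settled after the failures are known.

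**What to change.** In SAP 7.10, specify that device deficiencies are listed for all consented subjects in whom NIMBUS was introduced or its use attempted, whatever their mITT status. Show the stage of failure (insertion, advancement, deployment or retrieval) and state how many such subjects there were. In SAP 7.6, name the same set for adverse events. The mITT definition and the efficacy analyses do not change.

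The cost is one sentence in each section. Protocol 7.1.6 already puts the deficiency records on the eCRF for consented subjects. Three limits apply:

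- The documents do not show whether the eCRF has a field for stage of failure, so it may have to be taken from the description of the event.
- Protocol 7.3 requires adverse events only for enrolled eligible subjects, so for consented subjects who were not enrolled SAP 7.6 can report only what was recorded.
- Subjects who never consented remain outside any listing.

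The downside for the sponsor is a listing that may look slightly less favourable.
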